Study Rationale	
The use of positive end expiratory pressure (PEEP) in mechanical ventilation (MV) is important to reduce the collapse of alveoli between breaths. This atelectasis increases the patient's work of breathing and impairs oxygenation. In addition, atelectrauma can lead to ventilator-induced lung injury (VILI) through repetitive shear injury. There is a patient-specific response to PEEP titration, but PEEP titration is frequently not guided by individual patient data. There is a growing body of evidence that titrating PEEP according to estimated transpulmonary pressure (P_{tp}) measurements obtained by an esophageal balloon can improve outcomes, including measurements of lung function and time to liberation from tracheostomy in obese patients requiring prolonged mechanical ventilation, but also with trends toward decreased mortality and less time on the ventilator in survivors of ARDS. Notably, these trials have excluded patients with elevated intracranial pressure (ICP) or conditions where hypercapnia-induced elevations in intracranial pressure should be avoided [including intracranial bleeding, cerebral contusion, cerebral edema, mass effect (midline shift on CT scan), flat EEG for ≥ 2 h] for theoretical concerns of increasing ICP and decreasing cerebral perfusion pressure (CPP). Contrary to these concerns, small studies have shown that cerebral autoregulation is improved or unchanged while increases in intracranial pressure are small or nonexistent with increases in PEEP. Additionally, one case cohort study showed improved hypercapnia with use of esophageal balloon to guide PEEP. This study seeks to evaluate the safety of titrating PEEP to "optimal PEEP" based on P_{tp} as measured by an esophageal balloon in patients requiring mechanical ventilation who have CPP or ICP monitoring in place to correlate titrated PEEP with changes in ICP.

Study Objective(s)	To evaluate the safety of PEEP titration using esophageal balloon guided estimates of P_{tp} in neuro critical care patients.
Study Design	Non-inferiority trial comparing the effects of titrated PEEP compared to standard PEEP management on ICP, CPP, and hemodynamics in neurocritical care patients. All enrolled patients will have esophageal balloons placed with measurement of P_{tp} before and after intervention as well as baseline measurements of ICP, CPP, and MAP. All patients will undergo titration of PEEP based on P_{tp} measurements to an "ideal PEEP" (defined as end expiratory P_{tp} of 0-2). Measurements of ICP, and CPP, and MAP will be taken 5

	minutes after the titration of PEEP to evaluate the effect of PEEP titration on ICP, CPP, and MAP.
Subject Population key criteria for Inclusion and Exclusion:	
Inclusion Criteria: Adults (age \geq 18) admitted to the Neuro ICU of UNC Hospital requiring mechanical ventilation and with intracranial pressure monitoring in place.
 
Exclusion Criteria:
 
 1. Pneumothorax or pneumomediastinum 2. Life expectancy < 24 hours or expected to require mechanical ventilation for < 24 hours 3. Condition that precludes placement of an esophageal balloon (esophageal or nasopharyngeal pathology preventing insertion of the esophageal balloon catheter, severe thrombocytopenia or coagulopathy) 4. Pre-enrollment ICP > 20 mm Hg or refractory ICP elevation necessitating current pharmacological treatment 5. Pre-enrollment CPP < 60 mm Hg 6. Planned change in the external ventricular drain set point during the pre-intervention, intervention or post-intervention periods 7. Pregnancy 8. Incarceration 9. Variation in ICP > 2 cm H₂O in the 15 minutes prior to intervention.
Number Of Subjects	Approximately 25 subjects
Study Duration	Each subject's participation will last 1 hour. The entire study is expected to last 12 months.
Study Phases Screening Study Treatment Follow-Up	
(1) Screening: Screening for eligibility and obtaining consent
 
(2) Pre-Intervention: Baseline data collected, including ICP monitoring every 5 minutes for 15 minutes prior to the intervention to insure patients are at a steady state as it pertains to cerebral pressures. Patients with minimal ICP variation will then have an esophageal balloon placed to measure transpulmonary pressure.
 
(3) Intervention: PEEP titrated to "optimal PEEP" based on P_{tp}
 
(4) Post-Intervention: Data collection five minutes after intervention.
 
(5) Subject Completion/Withdrawal: Ventilator management will be returned to the primary critical care team to determine PEEP going forward. In patients who continue on the titrated level of PEEP, safety data will be collected for an additional 24 hours.

Efficacy/Safety Evaluations	This study is will use endpoints of ICP, CPP, and MAP to assess the safety of PEEP titration by P_{tp} measurements via

esophageal balloon. Determination of safety will be made based on the lack of a clinically significant increase in ICP, decrease in CPP, or decrease in MAP. All patients will have continuous hemodynamic and oxygenation monitoring, in addition to ICP/ CPP monitoring, per NSICU protocol to monitor patient safety. In patients who continue on the titrated level of PEEP after the intervention (decision made by the primary critical care team), ICP, CPP, hemodynamic, and oxygenation data will be recorded for 24 hours after the intervention to evaluate for any possible adverse events, and this data will also be reported.

Statistical and Analytic Plan

The trial is an interrupted time-series design non-inferiority trial evaluating “optimal PEEP” as determined by an esophageal balloon compared to baseline standard PEEP management. The primary outcome will be intracranial pressure with a non-inferiority limit of 4 mm Hg, analyzed with a non-inferiority design. CPP and MAP are secondary outcomes with non-inferiority margin of 10 mm Hg each.

DATA AND SAFETY MONITORING PLAN

The PI and Faculty Mentor will be responsible for maintaining patient data and ensuring accuracy of the data collected. All patient data will be collected using REDCap through the NC TraCS system. REDCap allows for immediate data validation and range setting to reduce the likelihood of erroneous data entry. Data created for analysis will be de-identified and secured on a password protected UNC School of Medicine network hard drive. All investigators will be trained on completing the electronic case report form.

Patient safety will be monitored with continuous cardiovascular monitoring by the critical care team. At the conclusion of the intervention, PEEP management will be returned to the primary clinical team. In patients who remain on the titrated level of PEEP, clinical information will be reviewed for 24 hours to identify and report any possible adverse events.

1 BACKGROUND AND RATIONALE

1.1 Introduction

This is an interrupted time-series design, non-inferiority trial to evaluate the safety of “optimal PEEP” in mechanically ventilated neurocritical care patients at UNC Hospital.

1.2 Description of Intervention

Trial participants will have placement of an esophageal balloon with manometry capabilities. Baseline measurements of P_{tp} , ICP, CPP, and MAP will be made at their baseline PEEP measurement. All patients will then undergo titration of PEEP based on P_{tp} measurements to an “ideal PEEP” with end expiratory P_{tp} of 0-2. Measurements of ICP, CPP, and MAP will be taken 5 minutes after the intervention. Data will be compared before and after intervention. At the conclusion of the intervention, PEEP management will return to the primary team. In patients continued on the “optimal” level of PEEP, patient data will be monitored for an additional 24 hours in order to report any possible adverse events.

1.3 Background (Relevant Literature and Data)

The use of PEEP in mechanical ventilation (MV) is important to reduce the collapse of alveoli between breaths. This atelectasis increases the patient’s work of breathing and impairs oxygenation. In addition, atelectrauma can lead to ventilator-induced lung injury (VILI) through repetitive shear injury (1). There is a patient-specific response to PEEP titration, but PEEP titration is frequently not guided by individual patient data. There is a growing body of evidence that titrating PEEP according to estimated transpulmonary pressure (P_{tp}) measurements obtained by an esophageal balloon can improve outcomes, including measurements of lung function and time to liberation from tracheostomy in obese patients requiring prolonged mechanical ventilation, but also with trends toward decreased mortality and less time on the ventilator in survivors of ARDS (2-4). These trials, as well as an ongoing multicenter trial using an esophageal balloon to titrate PEEP in patients with ARDS, have excluded patients with elevated intracranial pressure (ICP) or conditions where hypercapnia-induced elevations in intracranial pressure should be avoided [including intracranial bleeding, cerebral contusion, cerebral edema, mass effect (midline shift on CT scan), flat EEG for ≥ 2 h] for theoretical concerns of increasing ICP and decreasing cerebral perfusion pressure (CPP) (5). Contrary to these concerns, small studies evaluating use of PEEP in this patient population have shown that cerebral autoregulation is improved or unchanged while increases in ICP are small or nonexistent (6-10). Increases in PEEP without guidance of an esophageal balloon in one study caused a clinically insignificant rise in ICP in patients with normal ICP at baseline, however patients with elevated ICP (> 15 mm Hg) at baseline saw no increase in ICP as PEEP was increased (11). Additionally, one case cohort study showed improved hypercapnia with use of esophageal balloon to guide PEEP (3).

This protocol seeks to evaluate the safety of titrating PEEP to “optimal PEEP” based on P_{tp} as measured by and esophageal balloon in patients requiring MV who have CPP or ICP monitoring in place.

2 STUDY OBJECTIVE

The purpose of the study is to evaluate the safety of esophageal-pressure-guided PEEP management in neuro critical care patients.

2.1 Primary Objective

To determine that titration of PEEP to optimal PEEP does not result in clinically significant changes in ICP (defined as an increase in ICP > 4 mm Hg).

2.2 Secondary Objectives

- a. To determine that titration of PEEP to “optimal PEEP” does not result in clinically significant changes in CPP (defined as an increase in CPP > 10 mm Hg).
- b. To determine that titration of PEEP to “optimal PEEP” does not result in clinically significant changes in MAP (defined as a decrease in MAP > 10 mm Hg).
- c. To report any possible adverse events after titration of PEEP.

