3.3 Study Population

Inclusion Criteria: Adult patients (age ≥ 18) admitted to the Neuro ICU of UNC Hospital requiring mechanical ventilation and with ICP monitoring in place.

Exclusion Criteria:

1. Pneumothorax or pneumomediastinum
2. Life expectancy < 24 hours or expected to require mechanical ventilation for < 24 hours
3. Condition that precludes placement of an esophageal balloon (esophageal or nasopharyngeal pathology preventing insertion of the esophageal balloon catheter, severe thrombocytopenia or coagulopathy)
4. Pre-enrollment ICP > 20 mm Hg
5. Pre-enrollment CPP < 60 mm Hg
6. Planned change in the external ventricular drain set point during the pre-intervention, intervention or post-intervention periods
7. Pregnancy
8. Incarceration
9. Variation in ICP of > 2 cm H₂O in the 15 minutes prior to intervention.

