6.3 Statistical Methods

All endpoints will be described in term of means and standard deviation, with associated 95% confidence intervals, and median [Q1-Q3]

The change in ICP will be analyzed with a non-inferiority study: the ICP value after intervention will be considered equivalent to the ICP before intervention if the 95% upper bound of the change is lower than the non-inferiority margin of 4 mm Hg.

In a similar manner, the CPP and MAP values before and after intervention will be considered equivalent if the 95% lower bounds of the respective changes are higher than -10 mm Hg.

Should the 95% upper bounds of ICP be higher than 4, the effect of the intervention would be considered inconclusive. Similarly if the equivalence of CPP and MAP cannot be observed, the intervention will be reported inconclusive for these endpoints.

Adverse events will be reported.

By study design, all patients will be monitored in the ICU for the duration of the study and missing values are not expected. However, in the unlikely event that missing values would be present, the subjects will not be excluded and statistics will be calculated on all available data. The dataset for analysis will consist of all subjects regardless of protocol deviation, as an Intent-to-treat population.

Additional data points from the table above will be collected and tabulated using mean and standard deviation.

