7.2 Safety Monitoring

Data will be collected 5 minutes after the intervention, giving time for pressure equilibration from the ventilator and its effect on ICP, CPP, and MAP. Significant changes in these metrics, as defined above, will be reported as adverse events. At the conclusion of the intervention, PEEP management will be returned to the primary team. In patients whom they continue the “optimal PEEP” level, we will continue to evaluate for possible adverse events for an additional 24 hours, and this data will be reported. In addition to clinically significant changes in ICP, CPP, and MAP as defined above, additional adverse events that will be reported will include evidence of new barotrauma, change in pressor requirement, or change in HR to > 120 or < 50 .

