7.3 Adverse Event Reporting

“Possible Adverse Event” will be defined as a patient meeting any of the above parameters. Each possible adverse event will be reviewed by a UNC critical care physician who is independent of the study within 72 hours. After independent review, events considered to be likely or definitely related to the intervention will be submitted to the IRB for review.

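### Section 2.2a defines the harmful CPP change as a rise of more than 10 mm Hg, opposite to the synopsis and the Section 6.3 test, and the adverse-event rule in 7.2 and 7.3 points back to it

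*Combined protocol and SAP*

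**What the plan says.** Section 2.2 lists the secondary objectives. Item a concerns CPP, and the significant change is "defined as an increase in CPP > 10 mm Hg". Item b, the next line, concerns MAP, and there it is "defined as a decrease in MAP > 10 mm Hg".

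Elsewhere the direction for CPP is down:

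- Synopsis, Efficacy/Safety Evaluations: "Determination of safety will be made based on the lack of a clinically significant increase in ICP, decrease in CPP, or decrease in MAP".
- Section 1.3: a fall in CPP is one of the two theoretical concerns for which earlier trials excluded such patients.
- Section 6.3: CPP and MAP before and after are judged equivalent "if the 95% lower bounds of the respective changes are higher than -10 mm Hg".

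Section 7.2 then sets the reporting rule for ICP, CPP and MAP: "Significant changes in these metrics, as defined above, will be reported as adverse events". It repeats the back-reference for the 24-hour follow-up and adds new barotrauma, a change in vasopressor requirement, and heart rate above 120 or below 50. Under Section 7.3 a possible adverse event "will be defined as a patient meeting any of the above parameters". Each such event goes to an independent critical care physician within 72 hours, and those judged likely or definitely related go to the IRB.

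**The concern.** Two things follow if 2.2a is read as written.

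First, the secondary objective and its planned test address opposite directions. A lower confidence bound above −10 mm Hg says nothing about rises, so a trial that passes the 6.3 test would not have answered the objective as stated.

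Second, the error carries into safety reporting. Section 7.2 gives no section number for the definition it relies on, and 2.2a is the only place that defines a significant CPP change explicitly. A literal reader would send CPP rises above 10 mm Hg to independent review and would not count a CPP fall of any size as a CPP event. The trial's stated purpose is to assess safety.

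**Working it through.** **1. Direction, statement by statement**

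| Place | CPP change treated as harm |
|---|---|
| Synopsis, Efficacy/Safety Evaluations | decrease |
| Section 1.3 | decrease |
| Section 2.2a | increase > 10 mm Hg |
| Section 2.2b (MAP, for comparison) | decrease > 10 mm Hg |
| Section 6.3 | decrease (lower bound must exceed −10) |
| Sections 7.2 and 7.3 | whatever was defined earlier |

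Section 2.2a stands alone.

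**2. Is the sample size affected?** Section 6.4 gives 15 (ICP), 16 (CPP) and 18 (MAP) for a one-sided 95% interval and 80% power. These are reproduced by n = 2 × [(1.645 + 0.842) × SD / margin]²:

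- ICP: 2 × (2.487 × 4.4 / 4)² = 14.97, so 15.
- CPP: 2 × (2.487 × 11.3 / 10)² = 15.80, so 16.
- MAP: 2 × (2.487 × 11.8 / 10)² = 17.22, so 18.

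Only the size of the margin enters, so the CPP figure stays at 16 whichever direction is written. This is the per-group formula for two independent samples. Without the factor 2, as for paired changes, the results are 7.48, 7.90 and 8.61. The documents therefore do not establish that these SDs are SDs of within-patient change, so the calculation below uses both the stated values and half of them.

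**3. Which CPP falls escape the other pressure criteria?** Assume CPP = MAP − ICP. The MAP criterion is met only if MAP falls by more than 10, and the ICP criterion only if ICP rises by more than 4 (Section 2.1). The largest CPP fall that meets neither is 10 + 4 = 14 mm Hg, so falls between 10 and 14 can go unflagged.

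Example: MAP 80 to 71 (−9) and ICP 10 to 13 (+3) take CPP from 70 to 58 (−12). No pressure criterion is met. The final value lies below the protocol's own entry limit, "Pre-enrollment CPP < 60 mm Hg".

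**4. How often?** Assume normal, independent changes in MAP and ICP. An escape is ΔCPP < −10 with ΔMAP ≥ −10 and ΔICP ≤ 4. The mean shifts are assumptions.

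| SD of change, MAP / ICP | Mean change, MAP / ICP | CPP fall > 10 | Escapes, % of patients | Escapes, % of falls | Of 18 patients | CPP rise > 10 flagged only by 2.2a as written |
|---|---|---|---|---|---|---|
| 11.8 / 4.4 | 0 / 0 | 21% | 1.5% | 7% | 0.27 | 20% |
| 11.8 / 4.4 | −5 / +2 | 41% | 2.2% | 5.5% | 0.40 | 8% |
| 5.9 / 2.2 | 0 / 0 | 5.6% | 1.6% | 28% | 0.28 | 5.6% |
| 5.9 / 2.2 | −5 / +2 | 32% | 7.0% | 22% | 1.26 | 0.3% |

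Letting the MAP–ICP correlation run from −0.5 to +0.5 widens the escapes to 0.4–8% of patients and about 6–34% of falls. All these figures are before the vasopressor and heart-rate criteria, which would catch some of the escapes.

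**The case against.** The best reply is that this is a one-word slip whose intended direction is plain from four other places. Section 7.2 names no section, so its back-reference could equally mean the synopsis or 6.3. CPP is recorded before and after in every patient, monitored continuously and tested in the right direction. No stopping or treatment rule hangs on the definition, so only the classification of events is at risk. The limit of 60 mm Hg is an entry criterion and not a post-titration safety limit.

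Much of this stands. The adverse-event criterion is best called ambiguous, and reversed if 2.2a is taken literally. Crossing 60 mm Hg is not an event defined by the protocol; it only gives the example a scale.

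The magnitudes are also soft. If the three SDs in 6.4 are comparable and CPP = MAP − ICP, they imply a correlation of (11.8² + 4.4² − 11.3²) / (2 × 11.8 × 4.4) = 30.91 / 103.84, or about +0.3. The four cases then give 0.24, 0.42, 0.15 and 1.23 escapes among 18 patients, and the largest figure for rises flagged falls from 20% to 16%. The upper ends of the range in the working (34% of falls, 8% of patients) come only from a correlation of −0.5, which fits the stated SDs poorly.

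What does not stand is leaving the text alone. The 6.3 bound is a rule for a group mean and cannot classify one patient, and the synopsis sentence gives no threshold. That leaves 2.2a as the natural referent, and a reporting rule should not depend on staff correcting it as they read.

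**Conclusion.** The concern holds. Section 2.2a contradicts the synopsis, Section 1.3 and Section 6.3, and the adverse-event rule in 7.2 and 7.3 inherits the contradiction. The practical gap is small: CPP falls of more than 10 and up to 14 mm Hg made up of sub-threshold MAP and ICP changes, in the order of 0.3 to 1.3 of 18 patients under the independence cases. That size rests on CPP = MAP − ICP, normal changes, and SDs and mean shifts that the documents do not establish. The contradiction itself rests on no assumption. The CPP analysis, margin and sample size and the primary endpoint stand as they are. It should be fixed because it concerns a secondary objective and an adverse-event definition in a safety trial, but it does not threaten the trial's main result.

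**What to change.** In Section 2.2a, replace the word increase with decrease, so that the CPP objective agrees with the synopsis, with 2.2b's parallel wording and with the test in 6.3. In Section 7.2, replace both unnumbered back-references with a citation of Sections 2.1 and 2.2, so that the patient-level thresholds for ICP, CPP and MAP have one clear source. The cost is one word and a cross-reference. Data collection, analysis, margin and sample size do not change. If patients have already been enrolled, the recorded CPP values before and after titration, and the hourly values where collected, allow any CPP falls above 10 mm Hg to be identified retrospectively and put through the 7.3 review.

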3 INVESTIGATIONAL PLAN

3.1 Study Design

Noninferiority trial

3.2 Study Duration, Enrollment and Number of Subjects

Enrollment will continue until 18 subjects have been enrolled who require an increase in PEEP of at least 5 cm H₂O (based on P_{tp} at the time of enrollment). Based on a prior study which found 29% of participants were within 5 cm H₂O of optimal PEEP at the time of enrollment (2), we expect we will need to measure esophageal pressures on approximately 25 patients to find 18 patients who require titration of PEEP. Based on expected enrollment of 2-4 participants per month, the trial is expected to complete enrollment within 12 months. Each patient’s participation will last 1 hour; for the few patients who remain on higher PEEP per the request of the team, safety monitoring will continue for an additional 24 hours.

3.3 Study Population

Inclusion Criteria: Adult patients (age ≥ 18) admitted to the Neuro ICU of UNC Hospital requiring mechanical ventilation and with ICP monitoring in place.

Exclusion Criteria:

1. Pneumothorax or pneumomediastinum
2. Life expectancy < 24 hours or expected to require mechanical ventilation for < 24 hours
3. Condition that precludes placement of an esophageal balloon (esophageal or nasopharyngeal pathology preventing insertion of the esophageal balloon catheter, severe thrombocytopenia or coagulopathy)
4. Pre-enrollment ICP > 20 mm Hg
5. Pre-enrollment CPP < 60 mm Hg
6. Planned change in the external ventricular drain set point during the pre-intervention, intervention or post-intervention periods
7. Pregnancy
8. Incarceration
9. Variation in ICP of > 2 cm H₂O in the 15 minutes prior to intervention.

4 STUDY PROCEDURES

4.1 Screening/Enrollment

Daily screening of all intubated patients in the Neurosurgery ICU will be conducted by the research team. Intubated patients will be evaluated for the presence of ICP monitors. For patients meeting these criteria, chart review will be performed to evaluate for exclusion criteria. The primary clinical team will then be approached for permission to enroll prior to approaching families of patients for enrollment.

